## 5. CONSIDERATIONS FOR DATA ANALYSES AND DATA HANDLING CONVENTIONS

### 5.1. Number of Participants

A total of 2,000 participants are planned to be enrolled, consisting of 1,700 participants with COPD, 180 with chronic bronchitis but without fixed airflow limitation, and 120 never smoker healthy control. Specifically, COPD subjects will be classified using the GOLD grades I – IV (i.e. mild, moderate, severe and very severe). To better understand the disease progression of early stage COPD, i.e. GOLD I and II grades, COPD participants will be recruited in the following manner: GOLD I: 700, GOLD II: 700, GOLD III: 200, GOLD IV: 100 ([Figure 1](#)[Error! Reference source not found.](#)).

[figure not shown]
Figure 1 Study Population Schematic

More assessments will be conducted among the 400 Biomarker & Digital sub-cohort participants who will be all recruited from selected Type A hospitals. The sub-cohort consists of 50 never smoker healthy control, 100 chronic bronchitis (N never smoker: 25), 100 GOLD I (N never smoker: 25), 100 GOLD II (N never smoker: 25) and 50 GOLD III participants (N never smoker: 20) ([Figure 2 Sub-cohort Population Schematic](#)). In GOLD I-III grades, certain number of COPD participants with previous exacerbation history (i.e. exacerbators) will be recruited (target number of subjects are as follows - GOLD I: 60 exacerbators, GOLD II: 60 exacerbators, GOLD III: 30 exacerbators). Further, a proportion of those who are maintenance inhaler treatment naïve

will be recruited, aiming for: 10 participants who are maintenance inhaler treatment naive will be recruited among exacerbators and non-exacerbators in each GOLD I, II, III groups respectively (Figure 2). All patient population sizes are approximate and allow +/- 10% for feasibility.

**Figure 2 Sub-cohort Population Schematic**

## 5.2. Arm Definition

This is a non-drug interventional study, and the “arm” in this SAP refers to the participants’ health status at enrolment, i.e. Healthy Control, Chronic Bronchitis, COPD (GOLD grades I – IV).

## 5.3. Baseline Definitions

Unless otherwise specified, the baseline value will be the assessment with a non-missing value at Visit 1.

For EXACT/E-RS score and daily steps, the baseline is defined as the average value of D1-D7.

Unless otherwise stated, if baseline data is missing, no derivation will be performed, and baseline will be set to missing.

## 5.4. General Considerations in Statistical Analyses

Unless otherwise specified, continuous data will be summarized using descriptive statistics: n, mean, standard deviation (sd), median, minimum and maximum. Categorical data will be summarized as the number and percentage of participants in each category.

## 5.5. Examination of Covariates, Other Strata and Subgroups

### 5.5.1. Covariates and Other Strata

The potential covariates for statistical analyses may include type of subjects (i.e. GOLD I-IV, chronic bronchitis, healthy control), gender, smoking status, baseline FEV1, count of COPD exacerbations in the previous 12 months from baseline. For analyses where a baseline value (of the analysis variable) is available this will also be included as a covariate in model-based analyses, and baseline by visit interaction may be included depending on the model. [CC1]

[REDACTED]

[REDACTED]

### 5.5.2. Examination of Subgroups

Subgroup definitions in main cohort were listed as follows,

- Age (<65 years, >65 at baseline)
- Site (Type A and Type B Hospital)
- Smoking status (Baseline ever/never smoker)
- History of exacerbation in the preceding years (Any exacerbation/No exacerbation)
- Inhaled treatment naïve (Yes/No)
- Childhood respiratory disease (Yes/No)
- Biomass fuel exposure (Yes/No)
- Presence of chronic bronchitis (Yes/No)

## 5.6. Other Considerations for Data Analyses and Data Handling Conventions

Other considerations for data analyses and data handling conventions are outlined in the appendices:

Section	Component
12.1	Appendix 1: Protocol Deviation Management and Definitions for Per Protocol Population
12.2	Appendix 2: Schedule of Activities
12.3	Appendix 3: Assessment Windows
12.4	Appendix 4: Data Display Standards & Handling Conventions
12.5	Appendix 5: Derived and Transformed Data
12.6	Appendix 6: Reporting Standards for Missing Data
12.7	Appendix 8: Abbreviations & Trademarks

## **6. STUDY POPULATION ANALYSES**

Study population analyses will be based on the full population and sub-cohort population, unless otherwise specified.

### **6.1. Participant Disposition**

A summary of patient disposition, including screening status, reasons for screen failures and completers of each visit will be provided for the All Screened Population. In addition, the number of participants enrolled by site will be summarized by arm using the Full population.

A summary of the number of participants in each of the analysis set described will be provided.

A summary of study disposition including factors shown in study population schematic (Figure 1 and Figure 2, respectively) will be provided for Full and Sub-cohort Population, respectively.

Duration of study will be summarized by arm in Full Population and Sub-cohort Population in a same table, using mean(sd), median, Q1, Q3, min and max. For any participants, the duration of study is defined as the number of days from enrollment to study completion or study discontinuation, i.e.

$$\text{Duration} = \text{Date of Final Visit} - \text{Date of Visit 1} + 1$$

The “Final Visit” is defined as the last scheduled visit (including exacerbation visit), regardless of Outpatient visits.

### **6.2. Protocol Deviations**

Protocol deviations will be tracked by the study team throughout the conduct of the Study. Important protocol deviations (including deviations related to study inclusion/exclusion criteria, conduct of the trial, patient management or patient assessment) will be reviewed by study team before DBL and listed.

### **6.3. Demographics and Baseline Characteristics**

The demographic characteristics, including age, gender, race, ethnicity, highest education level, household annual income (grade), occupation, basic insurance and commercial insurance will be summarized by arms.

Vital Signs including height, weight, BMI, blood pressure and heart rate will be summarized by arms.

Smoking status, passive smoker, and smoking related details will be summarized by arms.

Health and lifestyle information, including heating, cooking at home and cooking at work will be summarized by arms in Full Population.

#### **6.4. Medical History**

COPD disease history, including duration, current COPD maintenance therapy, first-degree relative diseases history, number of exacerbations and inhaled maintenance treatment naïve will be summarized in COPD patients by COPD I-IV arms. Number of exacerbation will be summarised into the following category: 0, 1, 2 and >2, and the median will also be provided.

Lower respiratory infections history will be summarized in chronic bronchitis patients by full population/sub-cohort population. Number of respiratory infections will be summarised into the following category: 0, 1, 2 and >2, and the median will also be provided.

Summary of medical history, current co-morbid conditions, childhood respiratory disease and other related questions will be provided by arms.

Concomitant medications including history and during study will be summarized by arm.

### **7. EXACERBATION**

#### **7.1. Exacerbation**

A descriptive summary of exacerbation at 18 month and 30 month will be provided in COPD and Chronic Bronchitis patients for Full population and Sub-cohort population. Moderate, severe and moderate or severe exacerbation will be summarized by times of exacerbation [none, yes (1, 2, greater than 2)].

A generalized linear model assuming a negative binomial distribution will be used to estimate the exacerbation rate (95% CI) for COPD patients and chronic bronchitis patients in Full population, and then compare the exacerbation rate with GOLD I arm. Rate ratio (RR), 95% CI of RR and nominal P value will be provided for reference.

- **Covariates:** type of subjects (i.e. GOLD I-IV, chronic bronchitis), gender, smoking status, exacerbation history (moderate/severe), site (type of hospital), maintenance therapy (Y/N) and ICS containing (Y/N), Childhood chest disease (Y/N) and biomass fuel exposure (Y/N), age, and with offset logarithm of time on study.

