#### **9.2.6.2. Evening Diary (sub-cohort only)**

Participants in the sub-cohort will complete an eDiary each evening consisting of the 14 item EXACT and additional questions as described below. Participants will be trained to use the eDiary at baseline visit and will complete the diary each evening in line with SOA.

- Exacerbations of Chronic Pulmonary Disease Tool (EXACT) and Evaluating Respiratory Symptoms in COPD (E-RS: COPD)***

The Exacerbation of Chronic Pulmonary Disease Tool-Patient Reported Outcomes (EXACT) is a 14-item participant reported outcome instrument designed to capture information on the occurrence, frequency, severity, and duration of symptoms suggestive of an exacerbation of disease in participants with COPD. EXACT captures information on the severity of the respiratory and systemic manifestations of a COPD exacerbation as reported by the participant [[Leidy](#), 2013].

The Evaluating Respiratory Symptoms in COPD (E-RS: COPD) consists of 11 items from the 14-item EXACT instrument. The E-RS: COPD is intended to capture information related to the respiratory symptoms of COPD, i.e. breathlessness, cough, sputum production, chest congestion, and chest tightness. The E-RS: COPD has a scoring range of 0-40, with higher scores indicating more severe symptoms [[Leidy](#), 2014]. Three subscales of the E-RS: COPD are used to describe different symptoms: breathlessness, cough and sputum, and chest symptoms.

The EXACT questionnaire will be completed each day at bedtime in the daily digital diary during the pre-defined study period. EXACT events will be identified from the 14 EXACT questions. Changes in overall symptoms and in the subscales of breathlessness, cough and sputum, and chest symptoms will be measured using the E-RS: COPD subset of EXACT.

- Additional questions***

In addition to the collection of EXACT, participants will also complete 5 additional daily diary questions to provide the information on other symptoms suggestive of an exacerbation: sputum purulence (color), wheezing, sore throat, colds (nasal discharge and/or nasal congestion) and fever without other cause.

The additional symptoms questions, combined with EXACT responses to questions on dyspnea, cough and sputum quantity will be assessed in stream and used to trigger prompts to both site and patients about symptom changes that may be indicative of an exacerbation.

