**Figure 4 Exacerbation Detection Through Evening Diary Questions**

After completion of study procedures at the AECOPD Visit, the investigator will administer treatment for the exacerbation. Follow-up phone call(s) will be made by the investigator to the participant at least every 2 weeks until the AECOPD has resolved. No more than 2 AECOPD experienced during the study will be evaluated. If a participant experiences another exacerbation while on study, then they are to contact their regular physician for treatment.

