## 2.3. Study Design

## 2.4. Statistical Hypotheses / Statistical Analyses

This study is mainly descriptive with no formal inference associated with the study objectives. Nominal P-value may be provided as reference. 2-sided 95% confidence intervals will accompany all effect estimates.

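### Exacerbation rate ratios versus GOLD I pool diary-alerted and phone-followed participants in unequal shares by arm, so the chronic bronchitis and GOLD IV ratios could partly reflect detection

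*SAP*

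**What the plan says.** **The model.** SAP 7.1 estimates exacerbation rates for COPD and CB participants "in Full population, and then compare the exacerbation rate with GOLD I arm". It reports rate ratios with 95% intervals and nominal P values. The covariates are arm, gender, smoking, "exacerbation history (moderate/severe), site (type of hospital), maintenance therapy (Y/N) and ICS containing (Y/N"), childhood chest disease, biomass exposure and age, "and with offset logarithm of time on study". There is no sub-cohort or diary term, and the offset does not separate diary months from other months. SAP Table 2 defines the sub-cohort as part of the Full population.

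**Detection outside the sub-cohort.** Protocol sections 2, 5.1 and 9.2.4 provide for questions at clinic visits and 3-monthly calls, with a hospital information system (HIS) check where possible.

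**Detection inside the sub-cohort.** Members have all of the above. They also keep an evening diary for 6 months from Visit 1 and 6 months from Visit 3 (Protocol Table 1, note 9). Its answers are "used to trigger prompts to both site and patients about symptom changes that may be indicative of an exacerbation" (Protocol 9.2.6.2). Under Protocol 9.3 the investigator judges whether the worsening is a moderate/severe exacerbation and, if so, schedules a visit. Then: "After completion of study procedures at the AECOPD Visit, the investigator will administer treatment for the exacerbation". SAP 2.2 defines a moderate event by systemic corticosteroid and/or antibiotic treatment.

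**Sizes.** SAP 5.1 plans 180 CB participants, and "COPD participants will be recruited in the following manner: GOLD I: 700, GOLD II: 700, GOLD III: 200, GOLD IV: 100". On the sub-cohort it says: "The sub-cohort consists of 50 never smoker healthy control, 100 chronic bronchitis (N never smoker: 25), 100 GOLD I", followed by 100 GOLD II and 50 GOLD III. No GOLD IV participants are listed.

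**The concern.** A moderate event enters the count only if it is treated. A diary alert that brings the participant to an investigator can therefore add to the count as well as bring an event to notice sooner. A similar worsening outside the sub-cohort might go unreported or untreated. The Amendment 2 rationale itself notes that exacerbations often go unreported in mild to moderate disease. It refers to symptom-defined events, so it supplies no value for this endpoint.

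Unequal detection would matter little if it were spread evenly over the arms. It is not: CB is mostly sub-cohort, the GOLD I reference arm mostly is not, and GOLD IV has none. The rate of moderate/severe exacerbations is a listed endpoint under the first objective. A bias of this kind does not shrink as the sample grows.

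**Working it through.** **1. Planned totals.** The arms sum to 700 + 700 + 200 + 100 + 180 + 120 = 2,000 and the sub-cohort to 50 + 100 + 100 + 100 + 50 = 400, as stated. The plan gives no precision figure for the exacerbation comparison. Its only calculated sample size, for FEV1 decline, is 525 / 0.75 = 700 in each of GOLD I and II.

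**2. Sub-cohort share s of each arm (planned numbers)**

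| Arm | Sub-cohort / arm | s |
|---|---|---|
| CB | 100/180 | 55.6% |
| GOLD III | 50/200 | 25.0% |
| GOLD I | 100/700 | 14.3% |
| GOLD II | 100/700 | 14.3% |
| GOLD IV | 0/100 | 0% |

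With the 10% allowance on both numbers, CB runs from 90/198 = 45% to 110/162 = 68%, and GOLD I from 90/770 = 12% to 110/630 = 17%.

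**3. Spurious rate ratio when the true ratio is 1.** Let d be the factor by which the diary multiplies recorded events while it runs. This is an assumption; the documents give no value. The diary covers f = 12/30 = 0.4 of follow-up, so over the whole study a sub-cohort member records m = 1 + 0.4(d − 1) times as many events. The ratio versus GOLD I is

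(1 + s_arm(m − 1)) / (1 + 0.143(m − 1)).

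For d = 2, m = 1.4. CB is (1 + 0.556 × 0.4) / (1 + 0.143 × 0.4) = 1.222 / 1.057 = 1.16. GOLD III is 1.100 / 1.057 = 1.04. GOLD IV is 1 / 1.057 = 0.95.

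| d in diary months | m | CB | GOLD III | GOLD II | GOLD IV |
|---|---|---|---|---|---|
| 1.5 | 1.2 | 1.08 | 1.02 | 1.00 | 0.97 |
| 2 | 1.4 | 1.16 | 1.04 | 1.00 | 0.95 |
| 3 | 1.8 | 1.30 | 1.08 | 1.00 | 0.90 |

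**4. Do the planned covariates absorb it?** The sub-cohort comes only from Type A hospitals, so hospital type is a partial proxy. Assume the planned 2:1 split of Type A to Type B holds within each arm. Then 100/120 = 83% of Type A CB but 100/467 = 21% of Type A GOLD I would be sub-cohort. Fitting a negative binomial model with hospital type to expected counts at d = 2 moves CB only from 1.156 to 1.153 and GOLD IV from 0.946 to 0.947. Exacerbation history adjusts for prior risk, not for detection.

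**5. Would a sub-cohort covariate repair it?** If detection were the only difference, yes: every ratio returns to 1.00. But Protocol 5.2 targets 60, 60 and 30 exacerbators among the 100, 100 and 50 sub-cohort members in GOLD I, II and III, and sets no such target for CB. It defines an exacerbator by symptoms, treated or not, while the model adjusts for moderate/severe history, so some enrichment may remain. Take m = 1.4 and an assumed residual enrichment of 1.25 in COPD sub-cohort members only. They then record 1.4 × 1.25 = 1.75 times as many events, against 1.4 in CB. The fits to expected counts, with true ratio 1, give:

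| Model | CB versus GOLD I |
|---|---|
| As planned | 1.10 |
| Plus sub-cohort (Y/N) | 0.89 |
| Participants outside the sub-cohort only | 1.00 |

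The common coefficient is driven largely by the enriched COPD arms and over-corrects CB. At an assumed enrichment of 1.5 the covariate takes CB to 0.81.

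**The case against.** The case for leaving the plan alone has real force.

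- **The effect is unmeasured.** No document gives a diary-to-phone detection ratio or an exacerbation rate. This stands: direction and size depend on d being above 1.
- **The mechanism is bounded.** An alert leads to a visit only if the investigator judges that the definition is met. Visits are capped at two per participant, and later events go to the regular physician. HIS checks should pick up some treated events outside the sub-cohort. All of this narrows the gap. None of it equalises detection, and the cap is on visits, not on counted events.
- **CB is uncertain.** The exacerbation definitions are worded for COPD, so how fully the alert-to-treatment route operates in CB is not explicit. This stands, and it bears on the largest figure.
- **The study is descriptive.** There is no formal inference, although SAP 2.4 says that "2-sided 95% confidence intervals will accompany all effect estimates". This lowers the stakes but does not remove bias from a reported ratio.
- **The sub-cohort is summarised separately.** SAP 7.1 does so only as descriptive counts. The earlier RAP, reproduced after the SAP, marked an additional sub-cohort analysis, but its model had no sub-cohort term either.

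A reader might go further and infer that every ratio versus GOLD I is distorted. GOLD II has the same planned share as GOLD I, so its ratio is unaffected. A reader might also apply a doubling to all 30 months and obtain 1.36 for CB. The diary runs for 12 months, so an overall doubling would need 1 + 1/0.4 = 3.5-fold recording in diary months if the excess is confined to them.

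**Conclusion.** The concern holds conditionally. The model mixes two detection regimes in shares that differ widely by arm, and nothing in it separates them. If the diary raises recorded moderate/severe events, the CB ratio could be biased up and the GOLD IV ratio down. For a 1.5- to 3-fold rise confined to diary months, that is 8% to 30% up for CB and 3% to 10% down for GOLD IV. GOLD III moves up by 2% to 8%.

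These figures assume no true difference, a detection ratio common to all arms, planned rather than actual shares, and no residual enrichment. With residual enrichment in COPD the upward CB bias is smaller, as the 1.10 against 1.16 at the same detection ratio shows. The documents do not support saying that the ratios are in fact biased, or by how much. The change below is a cheap improvement to a descriptive analysis, not a correction of a demonstrated error.

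**What to change.** In SAP 7.1, add a supportive fit of the same negative binomial model restricted to participants outside the sub-cohort, who share one planned detection pathway in every arm. Footnote the Full-population rate-ratio table to say that sub-cohort participants had diary-triggered detection for 12 of the 30 months, and give the actual sub-cohort share by arm.

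The cost is SAP wording, one extra model run and a wider interval for CB, which falls to 180 − 100 = 80 planned participants. Taking exacerbators out of the COPD arms may also leave the remaining participants slightly depleted of them, so the two fits should be read together.

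A sub-cohort (Y/N) covariate should not be the lead remedy. If it is fitted, present it as a further sensitivity analysis and state that its coefficient mixes detection with selection.

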## 7.2. Clinically Important Deterioration (CID)

Clinically Important Deterioration (CID) is a new composite outcome (developed by GSK) for the prediction of future risk of long-term adverse outcomes. CID components are defined as:

- Exacerbation: An occurrence of a moderate/severe exacerbation.
- FEV1: Decrease of  $\geq 100$  mL in postbronchodilator FEV1
- CAT: Increase of  $\geq 2$  units in the CAT

CID event, or CID-positive (CID+) is considered as to have ANY of the 3 components.

A summary of participants in Full population who had at least 1 CID event in Baseline to Month6, Month6 to Month18 and Month18 to Month30 will be provided, the occurrence of CID and the components will be summarised. Considering the Spirometry onsite test may delay due to COVID, an additional rule of analysis window for post-baseline FEV1 is defined as planned visit date  $\pm 90$  days. If there's no available record, the result will be regarded as missing (no event).

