### 2.2. Study Objective(s) and Endpoint(s)

The following table shows the objectives and endpoints. More details about the endpoints are provided after the table.

Research Questions & Objectives	Endpoints
1. Evaluate whether the predictors of Chronic Obstructive Pulmonary Disease (COPD) disease progression identified in Western cohorts are applicable in China.	Main cohort 

Rate of decline in FEV1 and change from baseline in forced expiratory volume in 1 second (FEV1)

Research Questions & Objectives	Endpoints

 
• To evaluate disease progression in COPD and non-COPD participants over 2.5 years as assessed by lung function, exacerbation frequency, health status, lung high-resolution computed tomography (HRCT) scan, and changes in physical activity.
 
	
 
• Rate of decline in FVC and change from baseline in forced vital capacity (FVC)
 
• Rate of moderate/severe exacerbations*
 
• Change from baseline in COPD Assessment Test (CAT) score and rate of decline in CAT score
 
• Frequency of Clinically Important Deterioration (CID) and its components
 
• Death
 
 
Additional for sub-cohort
 
 
• Change in Evaluating Respiratory Symptoms in COPD (E-RS: COPD) scores
 
• Characterisation of Exacerbation of COPD Tool (EXACT) events
 
• Change from baseline in airway thickness by lung HRCT
 
• Change in lung density by lung HRCT
 
• Change in gas trapping
 
• Change in physical activity measures (e.g. Daily steps, bouts of activity per day)
 

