### 2.2.1. Additional information for endpoints of COPD progression

#### Exacerbation (Chapter 7)

Times of exacerbation 0-18m (baseline to Month 18, same for the followings) and 0-30m will be summarised. Rate of exacerbation (yearly) will be estimated based on negative binomial distribution at the end of study.

CID and its components are defined in [7.2](#). Percentage of participants who have any event(s) in 0-6m, 6-18m, 18-30m will be presented.

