## **Clinical feature Analyses (Chapter 8)**

Spirometry at each planned visit (baseline, Month 6, Month 18 and Month 30) and the post-baseline change from baseline will be summarised. FEV1 and FVC will be analysed using MMRM model. Analysis window for post-baseline visits of spirometry is defined as planned visit date  $\pm 90$  days. Spirometry results out-of-window will be regarded as missing.

Rate of change (decline) in FEV1 and FVC (yearly, unit ml/year) will be analysed at the end of study. All results regardless of the visit window will be included in the analyses.

COPD GOLD grade change, as the result of change of spirometry. Spirometry results out-of-window (visit window is  $\pm 90$  days) will be regarded as missing.

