## 4. ANALYSIS POPULATIONS

**Table 2. Summary of Study Populations**

Population	Definition / Criteria	Analyses Evaluated
All Screened	
The All Screened Population will consist of all participants who sign the ICF to participate in the clinical trial.
 
Participants in this population will be used for screen failure summary.
	
 
• Study Population
 

Full	The Full Population will consist of all subjects (except subject PPD ) who are enrolled in the study and attend Visit 1, and not withdraw informed consent.	
 
• Study Population
 
• Disease Progression Analyses
 
• Phenotypic Analyses
 
• Treatment Pattern and Healthcare Resource Utilization/Cost
 
• Safety Analyses
 

Sub-cohort	Sub-cohort is a subset of Full population. Subjects who are enrolled in the Biomarker & Digital sub-cohort and who provided at least one additional sub-cohort assessment.	
 
• Study Population
 
• Disease Progression Analyses
 
• Phenotypic Analyses
 
• Treatment Pattern and Healthcare Resource Utilization/Cost
 
• HRCT analysis
 

HRU	HRU is a subset of Full population. The following sites are not feasible to capture data by HIS, thus the patients enrolled from the following sites will be excluded from HRU analysis: 238160, 238222, 237965, 237971, 238155.	
 
• Treatment Pattern and Healthcare Resource Utilization/Cost
 

[figure not shown]
\*: Subject PPD cannot be categorized into either of the study arms (COPD patients, Chronic Bronchitis patients or Healthy Control), thus excluded from the Full population.

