#### Endpoint: FEV1 and FVC

Additional analysis of FEV1 and FVC will be provided in Full Population, described as followed.

Pre- and post-bronchodilator FEV1 at each visit, and their change from baseline will be summarized descriptively. N(missing), mean, sd, median, Q1, Q3, Minimum and Maximum will be provided. A same descriptive summary will be provided for FVC.

A line plot of pre- and post-bronchodilator FEV1 and FVC will be provided, showing the mean value of pre- and post-bronchodilator FEV1 and FVC at each visit on the same plot.

Analysis of Pre- and Post-bronchodilator FEV1 at each visit using mixed models with repeated measures (MMRM) will be provided. A same analysis will be provided for FVC. Details of MMRM is described in the following table.

Endpoint / Variables
Change of FEV 1 from baseline in milliliters (mL)

Change of FVC from baseline in milliliters (mL)
Model Specification

 
• The Mixed Models Repeated Measures (MMRM) analysis FEV1 or FVC at every on-site visit (6 months, 18 months and 30 months).
 
• Terms in the model: 
 
• Response: FEV1 or FVC change from baseline at each visit.
 
• Population: Full population
 
• Categorical: visit, type of subjects (i.e. GOLD I-IV, chronic bronchitis, healthy control), gender, smoking status, site (type of hospital), maintenance treatment (Y/N) and ICS containing (Y/N), Childhood chest disease (Y/N) and biomass fuel exposure (Y/N).
 
• Continuous: age, baseline FEV1, count of COPD exacerbations
 
• Interaction: type of subjects*visit, baseline*visit
 
• Repeated: visit
 
 
 
• The model will be fitted with an unstructured variance-covariance matrix. If the model fails to converge, then alternative covariance structures may be investigated.
 
• The Kenward and Roger method (KR) for approximating the denominator degrees of freedom and correcting for bias in the estimated variance-covariance of the fixed effects will be used.
 
• Comparison with Health Control will be provided.
 
• Models will be fitted for pre- and post-bronchodilator FEV1 and FVC, respectively.
 

Model Results Presentation

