### **8.3. COPD Disease Progression**

Disease status (healthy, chronic bronchitis, COPD [GOLD I-IV]) at each post-baseline visit in Full Population will be summarised by arm (reflecting baseline disease status). The participants who do not complete the visit will be regarded as missing at the certain visit. The rule for post-baseline COPD disease status is:

1. If post-bronchodilator FEV1(ml)/FVC(ml)  $\geq 70\%$ , the participants will be shown as “FEV1(ml)/FVC(ml)  $\geq 70\%$ ”, otherwise go to step 2;
2. If post-bronchodilator FEV1(ml)/FVC(ml)  $< 70\%$ , the participant will be regarded as COPD patient and the GOLD grade is defined as:  
GOLD 1: FEV1  $\geq 80\%$  of predicted;  
GOLD 2: FEV1  $< 80\%$  but  $\geq 50\%$  of predicted;  
GOLD 3: FEV1  $< 50\%$  but  $\geq 30\%$  of predicted;  
GOLD 4: FEV1  $< 30\%$  of predicted.

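### SAP 7.2 labels an absent in-window FEV1 both missing and no event without stating a denominator; taken as written, the FEV1 component of CID is biased low if any unmeasured participant declined

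*SAP*

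**What the plan says.** SAP 2.2 lists "Frequency of Clinically Important Deterioration (CID) and its components" among the main-cohort endpoints. SAP 7.2 makes a participant CID-positive on any of three components: a moderate/severe exacerbation, a post-bronchodilator FEV1 fall of at least 100 mL, or a CAT rise of at least 2 units. SAP 17.5.3 measures the FEV1 fall from baseline.

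The planned output is "A summary of participants in Full population who had at least 1 CID event in Baseline to Month6" and in the two later intervals, with the components summarised too. SAP 2.2.1 gives the statistic: "Percentage of participants who have any event(s) in 0-6m, 6-18m, 18-30m will be presented". The Full population (SAP Section 4, Table 2) takes in those "who are enrolled in the study and attend Visit 1, and not withdraw informed consent"; no post-baseline visit is needed.

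Because COVID may delay on-site spirometry, 7.2 adds a window of 90 days either side of the planned visit for post-baseline FEV1. With no available record, "the result will be regarded as missing (no event". SAP 2.1 announces the wider window as a change from the protocol but does not mention the no-event rule.

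Elsewhere the SAP leaves the same absence as missing:

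- SAP 2.2.1, clinical features: "Spirometry results out-of-window will be regarded as missing".
- SAP 8.1, FEV1 at each visit and change from baseline: "N(missing), mean, sd, median, Q1, Q3, Minimum and Maximum will be provided".
- SAP 8.3, disease status by arm: "The participants who do not complete the visit will be regarded as missing at the certain visit".

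**The concern.** *Missing* and *no event* are different instructions. Under the first, a participant without an in-window FEV1 leaves the denominator of the FEV1 component. Under the second, that participant stays in it and can never enter the numerator. Two programmers could produce different percentages from the same sentence. The population and the word *event* point towards the second reading, which treats not measured as not declined.

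The current SAP 7.2 plans only this descriptive summary for CID, so the percentage is the result. The missing-data sensitivity analysis in SAP 17.6.2 is multiple imputation for the MMRM and does not reach CID.

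**Working it through.** **Inputs.** The rule, window, population and statistic are those set out above. The documents state no CID rate, so there is no CID figure to reproduce. The only related number is the 25% drop-out in Protocol 10.1.3, which reproduces: 525/0.75 = 700 per GOLD I or II group. It is planned drop-out over the whole study, not the share without an FEV1 at a given visit. The following are therefore assumptions:

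- p, true FEV1-component rate: 20-50%
- m, share with no in-window FEV1: 5-35%
- q, share positive by CAT or exacerbation: 30-60%

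**Step 1: FEV1 component, missingness unrelated to decline.** Reported = p(1-m).

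| p | m = 5% | m = 10% | m = 25% | m = 35% |
|---|---|---|---|---|
| 20% | 19.0% | 18.0% | 15.0% | 13.0% |
| 30% | 28.5% | 27.0% | 22.5% | 19.5% |
| 40% | 38.0% | 36.0% | 30.0% | 26.0% |
| 50% | 47.5% | 45.0% | 37.5% | 32.5% |

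The shortfall is p × m, from 1 to 17.5 points. As counts, with 700 GOLD I participants, 525 measured and 210 declining among the measured: 210/700 = 30% under *no event*, 210/525 = 40% under *missing*.

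**Step 2: missingness related to decline.** Take m = 25% and an observed rate of 40% in the measured. Let r be the decline rate in the unmeasured divided by that in the measured. True rate = 0.75 × 0.40 + 0.25 × 0.40 × r.

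| r | True | Counted as no event | Among evaluable |
|---|---|---|---|
| 0 | 30% | 30% | 40% |
| 0.5 | 35% | 30% | 40% |
| 1 | 40% | 30% | 40% |
| 1.5 | 45% | 30% | 40% |
| 2 | 50% | 30% | 40% |

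The no-event figure is right only at r = 0, when nobody unmeasured declined. The evaluable figure is nearer the truth when r exceeds 0.5. At r = 0.5 the unmeasured hold 0.25 × 0.20 = 5 of the 35 points of true decline, so the break-even is 5/35 = 14.3% of decliners lacking an FEV1.

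**Step 3: composite.** Assume CAT and exacerbation are observed in everyone and independent of FEV1 decline. True = 1-(1-q)(1-p). No-event rule = 1-(1-q)(1-p(1-m)). Counting missing FEV1 as an event in the otherwise negative gives the upper bound 1-(1-q)(1-m)(1-p). With p = 40% and m = 25%:

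| q | True | No-event rule (lower) | Upper | Shortfall mp(1-q) | Width m(1-q) |
|---|---|---|---|---|---|
| 30% | 58.0% | 51.0% | 68.5% | 7.0 | 17.5 |
| 50% | 70.0% | 65.0% | 77.5% | 5.0 | 12.5 |
| 60% | 76.0% | 72.0% | 82.0% | 4.0 | 10.0 |

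**Step 4: would requiring all components to be observed be better?** Not reliably. Let FEV1 be missing in 35% of those positive by CAT or exacerbation and in 15% of the rest, with q = 50% and p = 40%. Restricting to participants with FEV1 gives (0.5 × 0.65 + 0.5 × 0.85 × 0.40)/(0.5 × 0.65 + 0.5 × 0.85) = 0.495/0.75 = 66.0%. The no-event rule gives 0.5 + 0.5 × 0.85 × 0.40 = 67.0%. The truth is 70.0%, and the upper bound is 0.5 + 0.5 × (0.15 + 0.85 × 0.40) = 74.5%. The restricted figure is the furthest off; the bounds contain the truth.

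**The case against.** The strongest reply is that the denominator is not written out. If *missing* governs it, the understatement of the component disappears. That stands, and it is why the bias is stated conditionally. It does not rescue the sentence, which still needs one meaning.

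Several things also limit the effect, and all of them stand:

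- Spirometry up to 90 days off schedule is kept.
- Protocol Section 2, Table 1 schedules spirometry at early withdrawal, and SAP 17.6.1 slots withdrawal visits into windows or summarises them separately, so some who leave can still supply an FEV1.
- Participants who withdraw consent are outside the Full population.
- Because change is measured from baseline, a sustained fall missed in one interval can be counted at the next in-window visit.
- CAT is collected by phone in all participants (Protocol 9.2.6.1) and exacerbations by phone in COPD and chronic bronchitis participants (Protocol Section 2), which shields the composite.

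A reader is also not left without any missing count. SAP 8.1 plans N(missing) for FEV1, and SAP 8.3 shows missing disease status by arm, so an evaluable percentage could be approximated from other tables. The CID table itself does not use these counts as its denominator.

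Finally, the study is descriptive, and FEV1 decline is analysed separately by MMRM and by random-coefficients models. That bounds the consequence; it does not correct this endpoint.

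**Conclusion.** The concern holds in conditional form. SAP 7.2 gives one absence two incompatible labels and no evaluable denominator. Taken as written in the Full population, it biases the FEV1-component percentage low whenever any unmeasured participant truly declined. Over the assumed ranges, with missingness unrelated to decline, the shortfall is 1 to 17.5 points for the component. For the composite at p = 40% and m = 25% it is 4 to 7 points, resting also on independent and fully observed CAT and exacerbation.

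A reader might infer more than the documents support:

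- *The component is understated in proportion to missing spirometry.* This is exact only if missingness is unrelated to decline, and only under the no-event reading.
- *The understatement is 25%.* That figure is whole-study planned drop-out. No per-visit missing-FEV1 rate is given.
- *Comparisons between arms are distorted in a known direction.* Equal true rates of 40% with 10% and 25% missing would be shown as 36% and 30%, but no missingness by arm is given, so the direction is unknown.
- *The rule also scores missing CAT or exacerbation data as no event.* The sentence before it concerns only the FEV1 window.

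**What to change.** In SAP 7.2:

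1. Replace the no-event label with *not evaluable* for the FEV1 component.
2. Report that component among participants with an in-window FEV1, with the number missing by arm and interval beside it. This matches SAP 2.2.1, 8.1 and 8.3.
3. For the composite, keep everyone positive by CAT or exacerbation. Show missing-as-no-event as a labelled lower bound, next to an upper bound that counts missing FEV1 as an event in those otherwise negative.
4. Do not make the percentage among participants with all components observed the main composite result. Protocol Section 2 requires 30 days of stability before every clinic visit (and 60 days after an exacerbation visit in the sub-cohort), so FEV1 availability may depend on exacerbations, and Step 4 shows that figure can be further off than the current rule.

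The cost is a wording change and a few table rows, with no new data. The composite carries a wider stated range: m(1-q), which is 12.5 points at m = 25% and q = 50%. The evaluable FEV1 percentage is not always nearer the truth (Step 2), so it should never appear without the missing count.
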